#### **5.4.4. C-SSRS**

Suicide-related thoughts and behaviours based on the C-SSRS will be listed by patient. Only time points and patients that show suicidal ideation/behaviour will be displayed (i.e., not all of the “no” responses will be displayed).

#### **5.4.5. QTcF**

The number of patients experiencing a maximum increase from baseline in QTcF interval will be summarised for each treatment according to the following categories: >30 ms and >60 ms. In addition, the number of patients with QTcF postdose values, according to the following categories: >450 ms, >480 ms and >500 ms, will be summarised by treatment.

Analyses of QTc using QTcF from ECG monitoring will be performed to judge the extent and/or risk of QT prolongation. An assessment of potential QTc prolongation will be performed using plots of PK data versus QTc values. Scatter plots will be created of QTcF versus LY3303560 concentration and change from baseline QTcF versus LY3303560 concentration (for timepoints where there is matched LY3303560 concentration and QTcF available). Placebo data will be included in the plot with concentration imputed to zero. The reference line of 450, 480, and 500 ms will be used for the QTcF versus concentration plot; while 10, 30 and 60 ms for QTcF change from baseline versus concentration plot. Analysis will be performed to assess the mean change in QTcF as a function of plasma drug concentration. The average of the triplicate QTcF measurements will be computed at each of the scheduled time points, and baseline will be the mean of the triplicate measurements collected prior to dosing at time 0 in each treatment period.

A mixed-effect model may be fitted to the QTcF change from baseline, with log –transformed plasma-drug concentration and dose included as fixed effects. The model will be run for the following ECG/PK time matched visits and time points in separate models; Visit 3(Day 1), Visit 8 (Day 27), Visit 9 (Day 57), Visit 13 (Day 169), Visit 19 (Day 337).

The following SAS code may be utilized:

```
proc mixed data=dose_sim;
by visit;
class patient;
model qtcrsult = pkresult / outp=resdat s cl alpha=0.1;
random patient;
ods output solutionf=sol;
run;
```

A second model may be run following the same model but combining all the visits together. Other time matched measures from non PK/ECG intensive days may also be considered for inclusion.

Further exploratory analyses may be conducted if required.

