## 5.6. Imaging Analyses

### 5.6.1. Flortaucipir SUVr

Whilst the following proposed analyses are not intended to test any hypotheses, they will be carried out to estimate the extent of changes from baseline of the flortaucipir F 18 SUVr after treatment with LY3303560.

The data will be analysed by an Analyses of Covariance (ANCOVA). Fixed effects of treatment doses (LY3303560 and placebo) will be fitted and a baseline covariate adjustment will be used.

The primary comparison is between LY3303560 and placebo for change from baseline in composite SUVr at last flortaucipir F 18 imaging visit. Covariates such as (but not limited to) APOE status, MMSE baseline score, diagnosis and age may be explored.

The following SAS code may be utilized:

```
proc mixed data=tau_sim;
  class patient treatment;
  model change_from_baseline_SUVR_month12 = treatment baseline_SUVR APOE, MMSE_baseline
  diagnosis age / outp=resdat s cl solution residual;
  lsmeans treatment /pdiff cl alpha=0.05;
  ods output lsmeans=lsmean1 diffs=diff1 covparms=cov1;
run;
```

In addition to the ANCOVA analysis, a Bayesian posterior probability may be computed for each LY3303560 dose compared to placebo, it is essentially a Bayesian interpretation of the results assuming a non-informative prior. The credible interval will be computed for each dose relative to placebo. For each dose of LY3303560, the posterior probability that the SUVr difference to placebo is less than or equal to a certain value (X) will be calculated as the appropriate tail area in the t distribution, e.g.,  $\text{Prob}(\text{LY xmg} - \text{Placebo} \leq X) = \text{prob t}((X - d) / \text{sed}, \text{df})$  where d is the estimated difference, sed is the standard error of the estimated difference and df is the degrees of freedom associated with this difference. This Bayesian inference is justified on the assumption of vague priors for all parameters in the model. Values of interest for X may be a 0%, 10%, 30%, 50% and 100% reduction in accumulation of tau compared to placebo.

This analysis may be repeated for SUVrs in individual and other composite brain regions if needed.

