### 5.6.2. Brain volume and functional connectivity

If data is available then changes in regional brain volume and functional connectivity in brain networks captured by MRI over the course of the study will be explored and summarised. MRI will be obtained every 8-12 weeks; therefore, an MMRM may be conducted fitting treatment and study visit and the interaction as fixed effects, the baseline will also be included and the baseline\*visit interaction will be assessed for potential inclusion. The following SAS code may be utilized for each relevant endpoint:

```
proc mixed data=MRI_sim;
  class patient treatment visit;
  model change_from_baseline_volume = treatment treatment*visit baseline_volume visit
  baseline*visit / outp=resdat s cl solution residual;
  random intercept/subject= patient type=un;
  lsmeans treatment*visit treatment /pdiff cl alpha=0.05;
  ods output lsmeans=lsmean1 diffss=diff1 covparms=cov1;
run;
```

Additionally, the relationship between LY3303560 serum exposure and imaging endpoints may be explored graphically or by a modeling approach.

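### The QTcF change-from-baseline model omits baseline QTcF, unlike the SAP's other baseline-referenced models; the precision lost is modest and depends on a correlation the documents do not give

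*SAP*

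**What the plan says.** SAP 5.4.5 makes the model optional: "A mixed-effect model may be fitted to the QTcF change from baseline". The text lists log-transformed "plasma-drug concentration and dose included as fixed effects". The sample code reads "model qtcrsult = pkresult / outp=resdat s cl alpha=0.1" with the random statement "random patient", so it has no dose term and shows no log transformation. The models are run separately by visit, with a possible second model that combines visits. Baseline QTcF is a covariate in neither the text nor the code.

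The baseline value exists. The same section states that "baseline will be the mean of the triplicate measurements collected prior to dosing at time 0 in each treatment period".

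Elsewhere the SAP does adjust. For the SUVr ANCOVA (5.6.1), "a baseline covariate adjustment will be used". For the brain-volume and connectivity MMRM (5.6.2), "the baseline will also be included and the baseline\*visit interaction will be assessed for potential inclusion". The cognition MMRM (5.7.2) also carries a pre-infusion baseline covariate, although its response is not stated to be a change.

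On placebo, SAP 5.4.5 sets concentration to zero for the scatter plots only. Protocol 9.5.2 plans no assay of placebo samples.

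**The concern.** A change score is negatively correlated with its own baseline, because measurement error in the baseline enters the change with the opposite sign. A random patient intercept puts that variation into the between-patient variance but does not remove it from comparisons between patients. Where the concentration slope rests mainly on such comparisons, leaving baseline out gives a noisier slope than the collected data allow.

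Visit 3 is that case. Protocol 2.2 schedules ECGs at 0, 0.5 and 2 h and PK samples at 0.5, 2, 4 and 8 h, so only 0.5 and 2 h match, and concentration changes little within a patient between them. What is at stake is the width of the 90% limits on a slope meant to help judge QT risk. The SAP gives no reason for treating this model differently from its other baseline-referenced models.

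**Working it through.** **1. The plan's own figures.** No QTcF standard deviation, correlation, power or precision is stated. The sample size reproduces: 2 cohorts x 8 = 16 completers, and 2 x 12 = 24 at most (Protocol 5.2 and 10.1). At 6 active to 2 placebo per cohort with placebo pooled, 2 x 2 = 4 placebo and 2 x 6 = 12 active are planned. If 24 were enrolled at the same ratio there would be 6 placebo.

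**2. Analytic variance ratio.** Write baseline = u + e0 and each post-dose value = u + e (plus any drug effect), with total variance 1 and rho = var(u). For the mean change over k matched times:

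- unadjusted variance: (1 - rho)(1 + 1/k)
- adjusted variance: (1 - rho)(rho + 1/k)
- ratio: (rho + 1/k) / (1 + 1/k)

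Estimating one more coefficient inflates the adjusted variance by about 1 + 1/(N - 4). That is 1.083 for N = 16 (all patients) and 1.125 for N = 12 (actives only). With k = 2:

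| rho | variance ratio | SE ratio, N = 16 | SE ratio, N = 12 |
|---|---|---|---|
| 0.5 | 1.0/1.5 = 0.667 | sqrt(0.722) = 0.850 | sqrt(0.750) = 0.866 |
| 0.7 | 1.2/1.5 = 0.800 | sqrt(0.867) = 0.931 | sqrt(0.900) = 0.949 |
| 0.8 | 1.3/1.5 = 0.867 | sqrt(0.939) = 0.969 | sqrt(0.975) = 0.987 |
| 0.9 | 1.4/1.5 = 0.933 | sqrt(1.011) = 1.006 | sqrt(1.050) = 1.025 |

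**3. Simulation of the two candidate models.** Random-intercept REML was run 1000 times per setting with 4 placebo, 6 at 70 mg and 6 at 210 mg. The assumptions not in the documents are a QTcF SD of 15 ms, rho from 0.5 to 0.9, and a 25% coefficient of variation of volume around 4 L (Protocol 3.2.1.1 reports 3 to 5 L). Model A follows the code: concentration only, placebo kept at 0. Model B follows the text: log concentration plus dose, actives only. Entries are the slope SE with baseline divided by the slope SE without it.

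| rho | A, Day 1 | B, Day 1 | A, later visit with trough | B, later visit with trough |
|---|---|---|---|---|
| 0.5 | 0.85 | 0.89 | 0.91 | 0.98 |
| 0.7 | 0.93 | 0.95 | 0.97 | 0.99 |
| 0.8 | 0.97 | 0.98 | 0.99 | 1.00 |
| 0.9 | 1.01 | 1.04 | 1.00 | 1.00 |

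The later-visit gain is smaller because the trough-to-peak change in concentration is within patient, and a patient-level baseline cannot sharpen that part. With no drug effect the mean slope was about 0 in every setting, so the omission causes no unconditional bias. The combined-visit model was not simulated.

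**4. Chance imbalance.** The SD of the placebo-active difference in baseline is SD x sqrt(1/4 + 1/12) = 0.577 x SD. This is 5.8, 8.7 and 11.5 ms for an assumed SD of 10, 15 and 20 ms. Only (1 - rho) of an imbalance carries into the unadjusted change contrast. Over SDs of 10 to 20 ms, a 1-SD imbalance moves that contrast by 2.9 to 5.8 ms at rho 0.5, 1.2 to 2.3 ms at 0.8 and 0.6 to 1.2 ms at 0.9.

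Whether this reaches the slope depends on the model. On Day 1 the correlation between slope and imbalance in model A is 0.37, 0.27, 0.22 and 0.11 at rho 0.5, 0.7, 0.8 and 0.9, and about 0 once baseline is added. In model B it is about 0 with or without baseline.

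**The case against.** The strongest reply is that this is a covariate preference in an optional model. The committed QTcF outputs are threshold counts and scatter plots, which the omission does not touch, and the SAP allows further exploratory QTcF work. This stands as an argument about importance. It is tempered by one fact: both Protocol 10.3.1.2 and SAP 5.4.5 commit to some analysis of mean QTcF change against concentration, and this mixed model is the only method the SAP specifies for it.

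A second reply is that averaging triplicates raises rho and so shrinks the gain. This also stands: at rho 0.8 the gain is 2 to 3%, and near 0.9 adjustment costs slightly more than it returns.

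A third is that the SUVr and MRI models compare treatments rather than estimate a concentration slope, so consistency alone is weak support. That is fair, but the regression-to-the-mean argument applies to any between-patient comparison of change scores.

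A reader might infer something stronger: that with about 4 placebo patients a chance baseline difference distorts the QT slope. The documents do not support that for the written model. Log of zero is undefined, the zero value is given for the plots only, and placebo samples are not planned for assay, so placebo drops out unless a substitution rule is added. The inference holds only for the code's concentration-only model with placebo at zero, and then only for the (1 - rho) share of the imbalance.

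**Conclusion.** The omission is real and minor. Baseline QTcF is absent from both text and code, the data are in hand, and the SAP's other baseline-referenced models use baseline. On Day 1, adding it would reduce the slope SE by about 11 to 15% at rho 0.5, 5 to 7% at 0.7 and 2 to 3% at 0.8, and would widen it by 1 to 4% at 0.9. At later visits with a trough the reduction is 2 to 9% at rho 0.5 and essentially nil by 0.8 to 0.9. These figures rest on assumed correlations and on 4, 6 and 6 patients.

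Two further readings should be resisted. The slope is not biased on average. Nor can the gain be expressed as power, because the plan sets no QTcF effect size and Protocol 10.3 plans no formal hypothesis tests. The more practical ambiguity in SAP 5.4.5 is that text and code disagree on log concentration and dose, and that the role of placebo in the model is unstated. That ambiguity decides whether baseline imbalance matters to the slope at all.

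**What to change.** If the model is fitted, add centred baseline QTcF as a fixed covariate in the per-visit and combined-visit models, in both the text and the SAS model statement. Use the same baseline that forms the change, and say which measurement that is, since the SAP refers to time 0 in each treatment period without defining the period. Report the slope, and the predicted mean change at mean baseline QTcF. In the same edit, make text and code agree on whether concentration is logged and whether dose is included, and state whether placebo patients enter the model and at what value.

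The cost is one line of text, one term in the code and one degree of freedom, with a slope SE at most about 1 to 4% wider if rho is near 0.9. No new data are needed. SAP 5.1 already says that a change to the planned analysis needs no protocol amendment and will be described in the study report.

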5.4. Scientific Rationale for Study Design

This study will investigate the safety, tolerability, PK and PD of multiple IV doses of LY3303560 in patients with MCI due to AD and mild to moderate AD. Only patients with evidence of amyloid deposition will be recruited into the study as it has been shown that

advanced stages of tau pathology are associated with the presence of amyloid (Scholl et al. 2016; Schwarz et al. 2016), and both amyloid and tau are defining pathologies of AD (Montine et al. 2012). The presence of amyloid deposition will be confirmed by amyloid PET imaging using National Institute on Aging and Alzheimer's Association work group consensus guidelines (Albert et al. 2011; McKhann et al. 2011).

Placebo is included as the control, in a blinded manner for investigator/site staff and patients, to allow an unbiased assessment of the safety and PD data generated.

Magnetic resonance imaging is commonly used to detect amyloid-related imaging abnormalities (ARIAs), which have been associated with anti-amyloid therapy. Both ARIA-E (vasogenic oedema) and ARIA-H (microhaemorrhage) have been reported after administration of several amyloid antibodies. While there is no evidence of imaging abnormalities with therapies targeting tau from the preclinical data for LY3303560 or from other tau therapeutics in the literature, MRI scans will be taken at predose, and thereafter at times specified in the Schedule of Activities (Section 2) after dosing with LY3303560 or placebo, in order to assess the potential for imaging changes, including, but not restricted to, vasogenic oedema and microhaemorrhage.

The inclusion of Japanese patients in this trial will facilitate the inclusion of Japanese patients in subsequent clinical trials.

The primary objective of investigating safety and tolerability of LY3303560 at steady state after administration of multiple IV doses will be evaluated, with evaluation of safety data from 8 patients (6 LY3303560: 2 placebo) in each cohort. It is anticipated that steady-state concentrations of LY3303560 will be achieved after approximately 4 months of dosing (4 doses), and so the minimum safety and PK data required to support future studies are up to Day 113.

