9.5.2. Bioanalysis

Samples will be analysed at a laboratory approved by the sponsor and stored at a facility designated by the sponsor.

Concentrations of LY3303560 will be assayed using a validated ELISA method. Analyses of samples collected from placebo-treated patients are not planned.

Bioanalytical samples collected to measure IMP concentrations will be retained for a maximum of 1 year following last patient visit for the study.

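### The concentration-QTcF model has no workable place for placebo and no time term, so a post-dose QTcF shift shared with placebo would be credited to the drug

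*SAP*

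**What the plan says.** SAP 5.4.5 makes a commitment: "Analysis will be performed to assess the mean change in QTcF as a function of plasma drug concentration". The only model it specifies for this is optional. It regresses QTcF change from baseline on log-transformed "plasma-drug concentration and dose included as fixed effects", separately at Visits 3, 8, 9, 13 and 19. The SAS statement printed beneath is "model qtcrsult = pkresult / outp=resdat s cl alpha=0.1", run by visit with a random patient effect. It shows no log and has no dose, treatment or time term. Then: "A second model may be run following the same model but combining all the visits together".

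On placebo, the same section says "Placebo data will be included in the plot with concentration imputed to zero" and gives no rule for the model. Protocol 9.5.2 adds: "Analyses of samples collected from placebo-treated patients are not planned". Protocol 5.4 gives the reason for having placebo, and applies it to safety as well as PD: "Placebo is included as the control, in a blinded manner for investigator/site staff and patients, to allow an unbiased assessment".

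Protocol Section 2.2 sets dosing-day ECGs at 0, 0.5 and 2 h. PK samples are at 0.5, 2, 4 and 8 h at Visit 3, with a time 0 sample added at Visits 8, 9 and 13. Matched pairs are therefore 0.5 and 2 h at Visit 3, and 0, 0.5 and 2 h at the other three visits.

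**The concern.** - **Placebo is lost.** The log of zero is undefined and no offset or rule is given. The slope is then fitted in active patients only, with no concurrent control.
- **Text and code disagree.** A programmer cannot follow both. The code could keep placebo at zero, but without a time term it still cannot separate concentration from time after dosing.
- **Pooling repeats the fault.** The second model has the same terms and adds none for visit.

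At Visits 8, 9 and 13 concentration goes from trough to peak exactly as the clock goes from predose to postdose. A QTcF change due to time of day, rest or the infusion procedure is then indistinguishable from a drug effect. A shift in the other direction could hide a real one.

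**Working it through.** **Inputs.** The plan gives no error rate or precision for this model, so there is no QTcF figure to reproduce. Its PK figures can be checked:

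- Average concentration at 210 mg: 1170 / 28 = 41.8 µg/mL, as in Protocol Table LMDD.2.
- Clearance: 210 / 1170 = 0.179 L/day (Protocol 3.2.1.1: about 0.2).
- With a volume of 4 L (Protocol 3.2.1.1: 3 to 5 L), k = 0.179 / 4 = 0.0449 per day, and the half-life is 0.693 / 0.0449 = 15.4 days (stated: 2 to 3 weeks).
- Steady-state trough/peak: exp(-28 × 0.0449) = 0.285, so ln(peak/trough) = 1.256.

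**Why the slope takes up the shift.** Concentration barely changes between 0.5 and 2 h. Within a patient, log concentration is thus close to a predose/postdose indicator. If only within-patient information counted, a 5 ms shift would give a slope of 5 / 1.256 = 3.98 ms per log unit, and the whole 5 ms would be credited to the rise from trough to peak. Differences in concentration between patients carry no shift and pull the figure down a little.

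**Simulation.** Patients: 6 at 70 mg, 6 at 210 mg, 4 on placebo. The true drug effect is zero, and the same shift is added at 0.5 and 2 h in all arms. Estimates are generalised least squares, b = (X'V⁻¹X)⁻¹X'V⁻¹y, where V holds a between-patient variance shared by all of a patient's records plus a within-patient variance. Assumed, because the documents give no values: SD 6 ms between and 7 ms within patients, concentration CV 25% with 10% residual, two-compartment PK (CL 0.2 L/day, V1 3 L, V2 2 L, Q 0.4 L/day). Pooling is over Visits 3, 8, 9 and 13.

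Of a 5 ms shift, the amount credited to the rise from trough to peak:

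| Model | Visit 8 | Visit 9 | Visit 13 | Pooled |
|---|---|---|---|---|
| Text (log concentration + dose) | 4.78 | 4.64 | 4.58 | 4.4-4.5 |
| Printed code, placebo = 0 | 3.96 | 3.78 | 3.68 | 4.2 |
| Proposed (see fix) | 0.00 | 0.00 | 0.00 | 0.00 |

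Probability that the slope's 90% interval lies wholly above 0 (nominal 5%), for shifts of 2 / 3 / 5 ms:

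| Model | Visit 13 | Pooled |
|---|---|---|
| Text | 19 / 31 / 61% | 40 / 67 / 97% |
| Printed code, placebo = 0 | 14 / 21 / 41% | 29 / 50 / 86% |
| Proposed | 5% | 5% |

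**Sensitivity.** Over SD pairs (between/within) 6/7, 4/8, 2/8 and 8/5 ms, CV 20-30% and trough/peak 0.14-0.37, the text model credits 78-97% of the shift at Visits 8, 9 and 13. With one-compartment PK from the documents' figures and SDs of 6/7, it credits about 4.0 of 5 ms at Visit 13, and the percentages are 18 / 30 / 59 (Visit 13) and 38 / 64 / 95 (pooled). With SDs of 4/6 and a 5 ms shift they are 69% and 99%.

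**Visit 3.** There is no predose PK sample, so the shift goes into the intercept and the slope is not biased. The predicted change at the peak still carries about 5 ms.

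**Dose term.** At Visit 3 concentration varies mainly between patients, and dose absorbs the threefold contrast. The log-concentration variance falls from (ln 3 / 2)² + 0.25² = 0.302 + 0.0625 = 0.364 to 0.0625, so the slope's standard error grows by about √(0.364 / 0.0625) = 2.4. Simulated values are 2.2-2.8 at Visit 3, but only 1.02-1.27 at Visits 8, 9 and 13 (1.39 at the extreme) and 1.01-1.13 pooled (1.26 at the extreme).

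**The case against.** The model is optional, the study plans no formal testing, and no escalation or stopping rule uses the slope. Placebo stays in the categorical QTcF counts, the scatter plots and the summaries by time point, where a common shift could be seen. The shift is an assumption; if there is none, there is no bias. All of that is true. It keeps this from being a critical fault and makes the size conditional. But these outputs do not correct the slope or its interval, and no other model is specified for an analysis the SAP says will be done.

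The strongest point is precision. At the 210 mg peak the placebo-corrected standard error is about 3.9 ms pooled (4.8 at one visit), against 2.6 (3.1) uncontrolled. Even if the uncontrolled estimate carries the whole shift, its root mean squared error is lower until the shift exceeds √(3.9² - 2.6²) = 2.9 ms pooled, or √(4.8² - 3.1²) = 3.7 ms at one visit. That trade-off is real with 4 placebo patients. It does not rescue the interval, which is narrower but centred on drug effect plus shift.

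The SAP also lets time-matched data from other days be added. In one run this cut the share credited at Visit 13 from about 83% to 38%, mainly through follow-up visits. It did not lower the rate at which the interval excludes zero.

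**Conclusion.** The concern holds and the model should be changed. Three faults can be read directly from the documents: placebo has no place in the log model, text and code conflict, and neither has a time term. The bias at Visits 8, 9 and 13 and in the pooled fit follows from the sampling schedule. Its size depends on the assumed shift. For 2-5 ms, the text model gives a false positive slope in 19-61% of trials at Visit 13 and 40-97% pooled; the printed code with placebo at zero gives 14-41% and 29-86%. The SDs and concentration CV are also assumptions and move these percentages, but the conclusion held in every setting tried. The Visit 3 slope is not affected in this way. The cost of the dose term is a secondary matter, material only at Visit 3.

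**What to change.** Make the pooled model the primary concentration-QTcF model, and make text and code agree:

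- **Response:** change from the single Day 1 (Visit 3) predose triplicate mean.
- **Fixed effects:** untransformed concentration with placebo = 0, an active/placebo indicator, nominal visit-by-time, and baseline QTcF. No dose term.
- **Random effect:** patient intercept.
- **Code:** `class patient active visit time; model dqtcf = conc active visit*time base_qtcf / s cl alpha=0.1; random intercept / subject=patient;`
- **Report:** placebo-corrected change with 90% interval at each dose's geometric mean Cmax.
- **Checks:** residual plots for linearity, and a log-concentration fit in active patients as a sensitivity analysis.

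Three clarifications belong with this. First, state that time 0 in each treatment period means Day 1 predose. With a per-visit baseline that keeps the predose rows, which are zero by construction, a model with linear concentration, treatment and time terms showed 9-11% pooled instead of 5%. Second, correct Visit 8 from Day 27 to Day 29, as in Protocol Section 2.2. Third, check Visit 19 against that schedule: its ECG and PK cells are blank in the copy read here, which may be only a table-extraction effect.

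The cost is SAP text and code; placebo ECGs are already scheduled at the same times. Linearity in concentration becomes an assumption, and the 90% interval at the 210 mg peak will be about ±1.645 × 3.9 = ±6.4 ms. The SAP should say so.
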